- Reason for discontinuation
- Unscheduled lens replacement
- Reasons for unscheduled lens replacement including lens damage.

4. General Statistical Considerations

Continuous data will be summarized descriptively by n, mean, standard deviation (SD), median, minimum (Min) and maximum (Max). Minimum and maximum will be presented to the same number of decimal places as the raw data, mean and median will be presented to 1 more decimal place than the raw data, and standard deviation will be presented to 2 more decimal places than the raw data.

Categorical data will be summarized descriptively by frequency: n (%). The denominator for all percentages will be the number of subjects (or eyes as applicable) available, once pooled, within that treatment group for the analysis set of interest, unless otherwise indicated. Percentages will be presented to 1 decimal place and will not be displayed for zero frequencies. A row denoted “Missing” will be included in count tabulations where necessary to account for missing values.

All data summaries and statistical analyses will be performed using the SAS software version 9.3 or higher (SAS Institute, Cary, NC).

All planned analysis will be conducted with an overall type I error rate of 5%. Unless otherwise specified, all statistical tests will be 2-sided.

P-values will be rounded to 3 decimal places. P-values that round to 0.000 will be presented as '<0.001' and p-values that round to 1.000 will be presented as '>0.999'.

Study day of an event that occurred after or on the first Fitting date will be calculated as Event Date – First Fitting Date + 1.

Study day of an event that occurred before the first dose date will be calculated as Event Date – First Fitting Date.

Baseline is last assessment obtained prior to the insertion of the test or control lenses, unless otherwise specified. Some subjects may have up to four baseline evaluations if a damaged lens needs to be replaced and/or due to failure to fulfil inclusion criteria and/or due to fulfilment of exclusion criteria. In this case, the last baseline evaluation will be considered in the descriptive summary and analysis. For subjects enrolled but not randomized the last non-missing assessment will be taken as baseline.

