4.1. Sample Size

Assuming a perfect correlation between left eye visual acuity and the right eye visual acuity (worst case scenario), the total sample size (n) required to achieve 85% power with two-

sided type I error of 0.05 was calculated for different scenarios of mean difference (Δ = K-Lens – Placebo) and common standard deviation (σ) in the two arms. The results are summarized in the Table below:

Table 2: Sample size for different scenarios of mean Δ and σ

Δ	σ	n
0	0.05	15
0	0.01	45
0.04	0.05	33
0.04	0.1	117

The sample size calculation was conducted using the PROC POWER Procedure (SAS/STAT 14.1, SAS Institute, 2015) for two-sample means with allocation weight of 2:1.

The sample size of 120 subjects is considered sufficiently large to test for non-inferiority with a minimum statistical power of 85% and two-sided type I error of 0.05.

The plan is to enroll 132 eligible subjects with a target completion of 120 subjects (80 subjects in K-Lens and 40 subjects in Placebo).

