The log-likelihood ratio test will be used to test for the homogeneity between the residual covariance structures across treatment groups. The Kenward and Roger method will be used to calculate the denominator degree of freedom.²⁵

The null and alternative hypotheses for non-inferiority of K-Lens relative to Placebo are as follows:

$$H_0: \Delta \geq 0.1$$
$$H_A: \Delta < 0.1$$

where Δ is the mean difference in visual acuity between K-Lens and Placebo (K-Lens minus Placebo). The non-inferiority test will be based on the least-square mean difference (K-Lens minus Placebo) and corresponding 95% confidence interval calculated using the final selected model. The upper bound of the 95% confidence interval will be compared to the non-inferiority margin of 0.1 LogMAR. If the upper bound is less than 0.1, K-Lens will be considered non-inferior to Placebo with respect to visual acuity.

The following code will be used to run the mixed model.

```
proc glimmix data = dataset plots=ResidualPanel;
class treatment siteid subjid eye;
model logmar = treatment/ DDFM=KenwardRoger S;
random intercept /subject = siteid;
random eye / type=matrix_cov subject=subjid(siteid) group = treatment
residual;
lsmeans treatment / diff=control('Placebo') cl;
covtest 'Common Variance' Homogeneity;
ods output ParameterEstimates=parms Covtests=mixcovtest
CovParms=mixcovp diffss=diffs lsmeans=lsmeans;run;
```

Where:

- “Treatment” is the treatment group variable (K-Lens/Placebo);
- “Siteid” is the investigator site identifier;
- “Eye” is the variable to identify which eye the observation belongs to (left/right);
- “Subjid” is the subject identifier;
- “Matrix_cov” is the covariance structure (UN/CS) between the left eye visual acuity and right eye visual acuity.

If the hypothesis of homogeneity is accepted (chi-square test p-value > 0.05) the syntax “group = treatment” and the ‘covtest’ statement will be omitted from the final model.

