12.3. SAS Code for Sensitivity Analysis

The following SAS code will be used to generate the sensitivity analysis for the difference in visual acuity logMAR score (K-Lens versus Placebo), using a MI process for imputation of missing data.

Multiple imputation phase

```
proc mi data= yyyyyyy nimpute=20 seed=51343672 out=outmi ;
  class SITEID TREATMENT;
  var SITEID TREATMENT LOGMARV1_OD LOGMARV1_OS LOGMARV2_OD LOGMARV2_OS;
  fcs discrim(SITEID TREATMENT /classeffects=include) reg (LOGMARV1_OD LOGMARV1_OS LOGMARV2_OD
LOGMARV2_OS /details);
run;
```

In case the analysis of the missing data will show a monotone pattern, the same procedure will be executed with the MONOTONE statement.

```
proc mi data= yyyyyyy nimpute=20 seed=51343672 out=outmi ;
  class SITEID TREATMENT;
  var SITEID TREATMENT LOGMARV1_OD LOGMARV1_OS LOGMARV2_OD LOGMARV2_OS;
  monotone discrim (SITEID TREATMENT /classeffects=include) reg (LOGMARV1_OD LOGMARV1_OS
LOGMARV2_OD LOGMARV2_OS /details);
run;
```

where LOGMARV1_OD is the logmar score at the last visit, excluding unscheduled, prior to visit 2 for the right eye;
LOGMARV1_OS is the logmar score at the last visit, excluding unscheduled, prior to visit 2 for the left eye;
LOGMARV2_OD is the logmar score at visit 2 for the right eye;
LOGMARV2_OS is the logmar score at visit 2 for the left eye;
SITEID is site identifier within each study;
TREATMENT is the treatment variable (K-Lens/Placebo);

Analysis by imputation at each visit

```
proc glimmix data = outmi;
by _imputation_;
class treatment siteid subjid eye;
model logmar = treatment/ DDFM=KenwardRoger S;
random intercept /subject = siteid;
random eye / type=UN subject=subjid(siteid) group = treatment residual;
lsmeans treatment / diff=control('Placebo') cl;
covtest 'Common Variance' Homogeneity;
ods output ParameterEstimates=mixparms Covtests=mixcovtest CovParms=mixcovp diffss=diffs
lsmeans=lsmeans;
run;
```

If the hypothesis of homogeneity is accepted (chi-square test p-value > 0.05) the syntax “group = treatment” and the ‘covtest’ statement will be omitted from the final model.

The model will take into account using UN covariance matrix for each imputation dataset. In case the algorithm will not converge with the UN for a particular dataset, then the CS matrix will be used for such imputation dataset. This will be reviewed on a case by case basis.

Results combined for the inference at each timepoint and visit

```
proc mianalyze data=diffs;
modeleffects estimate;
stderr stderr;

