ods output parameterestimates=parest;
run;

proc mianalyze data=lsmeans;
by treatment;
modeleffects estimate;
stderr stderr;
ods output parameterestimates=parest_lsmeans;
run;
```

where SITEID is site identifier within each study;
SUBJID is subject identifier;

TREATMENT is the treatment variable (K-Lens/Placebo);
LOGMAR is visual acuity logMAR score at Visit 2.

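### SAP 12.3 pools the imputed fits without their Kenward-Roger degrees of freedom, so the sensitivity interval is about 1 to 1.6% too narrow, and it omits the step that passes imputed scores to the model

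*SAP*

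**What the plan says.** SAP section 8 plans three looks at the primary endpoint: the per-protocol primary analysis, a supportive repeat on mITT with missing scores left missing, and a multiple-imputation sensitivity analysis on mITT. The third has its own 95% interval and non-inferiority flag. Section 8 refers to Appendix 12.3 for the code.

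The appendix has three stages:

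- **Imputation.** PROC MI imputes four columns, one per eye and visit. For example, "LOGMARV2_OD is the logmar score at visit 2 for the right eye". The VAR list holds these four, site and treatment.
- **Analysis.** The next step is "proc glimmix data = outmi", by imputation, with response `logmar`, class variable `eye` and Kenward-Roger degrees of freedom. No step in between creates `logmar` or `eye`. A closing note says "LOGMAR is visual acuity logMAR score at Visit 2".
- **Pooling.** "proc mianalyze data=diffs" combines the treatment differences, and a second call combines the arm LS means. Both pass only the estimate and its standard error. Neither has an EDF= option.

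For the primary model, SAP 8.1 states "The Kenward and Roger method will be used to calculate the denominator degree of freedom", and its decision rule is "If the upper bound is less than 0.1, K-Lens will be considered non-inferior to Placebo with respect to visual acuity".

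**The concern.** Two things in the appendix code do not do what section 8 describes.

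1. **Pooling.** Each fit produces finite degrees of freedom, but the pooling call never receives them. Rubin's rule then reflects only the finite number of imputations. With little missing data the multiplier is close to the normal 1.960, whereas the primary analysis uses a t quantile. For the same estimate and standard error, the sensitivity interval would be shorter than the primary one. In a non-inferiority test that is the lenient direction.
2. **Data flow.** The imputed values sit in the `_OD` and `_OS` columns, while the model reads a different variable. If they are not carried across, the imputation has no effect on the result.

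This is the only planned analysis that fills in missing primary scores. The primary set is limited to subjects who completed all visits, and the plan allows for 132 randomized and 120 completing, a loss of 12/132 = 9.1%.

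**Working it through.** **The plan's own figure.** The SAP gives no number for the imputation interval. The nearest is Table 2 in SAP 4.1: n = 117 for Δ = 0.04 and σ = 0.1, at margin 0.1 and 2:1 allocation, "with a minimum statistical power of 85% and two-sided type I error of 0.05".

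- At 78/39, SE = 0.1 × √(1/78 + 1/39) = 0.01961 and the non-centrality is (0.10 − 0.04)/0.01961 = 3.06.
- With t(115) = 1.981, power is 85.9%. At n = 114 it is 84.9%, so 117 is reproduced.
- A normal approximation would give 114. The plan's own sizing therefore uses finite degrees of freedom.

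**Inputs for the pooling check**

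| Input | Value | Source |
|---|---|---|
| Imputations, m | 20 | SAP 8 and 12.3 |
| Randomized | 88/44 | SAP Table 1 |
| SD | 0.10 | largest σ in SAP Table 2 |
| Eye correlation | perfect | SAP 4.1, its worst case |
| Complete-data df, common variance | 132 − 2 = 130 | assumed |
| Complete-data df, separate arm variances | 86 (Welch) | assumed |
| Share of total variance due to missingness, λ | 0 and 0.09 | assumed; 0.09 is about the planned loss |

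Welch df, with equal variances in the arms: (1/88 + 1/44)² / [(1/88)²/87 + (1/44)²/43] = 86.1.

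SE = 0.1 × √(1/88 + 1/44) = 0.01846.

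**Nothing missing.** The coded multiplier is 1.960; the primary model would use t(130) = 1.978 or t(86) = 1.988.

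- Coded half-width: 1.960 × 0.01846 = 0.0362.
- Finite-df half-width: 1.978 × 0.01846 = 0.0365, or 1.988 × 0.01846 = 0.0367.
- Shortfall: 1 − 1.960/1.978 = 0.9%, or 1 − 1.960/1.988 = 1.4%. In logMAR this is 0.0003 to 0.0005.

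**λ = 0.09**

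- Without EDF: df = (m − 1)/λ² = 19/0.0081 = 2346, quantile 1.961.
- With EDF = ν: ν_obs = ν(ν + 1)/(ν + 3) × (1 − λ), combined as 1/(1/2346 + 1/ν_obs).
- ν = 130: ν_obs = 116.5, pooled df 111, quantile 1.982, shortfall 1.0%. Deducting five further df for six sites (ν = 125) gives 1.1%.
- ν = 86: ν_obs = 76.6, pooled df 74, quantile 1.992, shortfall 1.6%.
- With total SE 0.01846/√0.91 = 0.01936, the half-width is short by 0.0004 to 0.0006 logMAR.

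**Coverage.** At λ = 0.09 the nominal coverage of the coded interval is 94.8% (ν = 130) or 94.6% (ν = 86). A simulation (132 subjects, 1,500 replicates, both eyes averaged, site as a fixed effect, assumed correlations) gave the following coverage without and with EDF:

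| Missing | Eye correlation | Visit correlation | Without EDF | With EDF |
|---|---|---|---|---|
| 9.1% | 0.70 | 0.60 | 95.3% | 95.5% |
| 9.1% | 0.95 | 0.60 | 94.5% | 94.9% |
| 15% | 0.70 | 0.60 | 95.7% | 96.2% |
| 25% | 0.70 | 0.30 | 94.5% | 95.0% |

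The Monte Carlo standard error is √(0.95 × 0.05/1500) = 0.6 percentage points, so all eight figures are near 95%.

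**Data flow, read line by line**

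- If the input has one row per subject, as the `_OD`/`_OS` columns imply, `logmar` and `eye` are not in `outmi` and the model step stops.
- If the input also carries `logmar` and `eye`, they pass through unimputed. A dropout's `logmar` stays missing in all 20 copies, the 20 fits are identical and the between-imputation variance is 0. The estimate is then that of the supportive mITT analysis.

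**The case against.** The strongest reply is that neither point threatens a conclusion.

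**On pooling.** The effect is about 0.0005 logMAR against a margin of 0.1, and simulated coverage stays near 95%. In the least favourable planning scenario (Δ = 0.04, σ = 0.1) the expected upper bound with nothing missing is 0.04 + 0.0362 = 0.0762 as coded, against 0.0765 to 0.0767. This stands as to size. It does not make the code right: SAP section 4 says "All planned analysis will be conducted with an overall type I error rate of 5"%, the lenient direction is known in advance, and the correction is one option per call.

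**On data flow.** The SAP leaves little doubt about what was meant. It defines the two Visit 2 columns, defines LOGMAR as the Visit 2 score, and in 8.1 defines Eye as left or right. Only one reshape fits. The printed code is partly a skeleton: the input name is a placeholder, and no sort is shown before the LS means are read by treatment. This largely stands, so the gap is one of specification with evident intent.

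A reader might infer that the imputation will silently be lost. The documents do not support that. A file with one row per subject produces a visible error, and the silent branch needs a mixed layout that neither document describes. Even then, agreement with the supportive mITT estimate and a between-imputation variance of 0 would show it.

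A reader might also infer that the analysis both fails and gives too narrow an interval. These exclude each other: if the step stops there is no interval, so the EDF= point applies only once the code runs.

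**Conclusion.** Both points hold, at modest size, and both concern the sensitivity analysis only. The primary decision uses the per-protocol set with Kenward-Roger degrees of freedom and does not pass through this code.

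The missing EDF= is an error in the coded rule. On the assumed degrees of freedom it narrows the interval by 0.9 to 1.4% with nothing missing and by 1.0 to 1.6% at λ = 0.09. A complete-data value as low as 43 (placebo arm alone) would raise this only to about 3%. The flag could change only if the upper bound fell within about 0.0005 of 0.1. A reader might infer that the sensitivity analysis is materially easier to pass than the primary one. That does not follow: the comparison holds only for the same estimate and standard error, whereas the two analyses use different populations and handle missing scores differently.

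The missing reshape is the more basic gap, because without it the imputed scores never enter the model, but the SAP's definitions make the intended step clear.

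The percentages rest on the assumed degrees of freedom and, at λ = 0.09, on the assumed share of variance. The logMAR figures also rest on SD 0.10 and perfect correlation between eyes; at SD 0.05 they halve.

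**What to change.** In SAP Appendix 12.3:

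1. After PROC MI, add a step that writes two rows per subject per `_imputation_`, with `logmar` equal to `LOGMARV2_OD` for the right eye and `LOGMARV2_OS` for the left, and have the model read that file.
2. Add EDF= to the pooling call for the differences, set to the Kenward-Roger df of the treatment difference. State beforehand how one value is chosen if it varies across imputations.
3. Add EDF= to the LS-means call, set to the Kenward-Roger df of each arm's LS mean. The df of the difference should not be reused here: an arm mean carries the random site variance and has its own df.
4. Add a programming check that the between-imputation variance is above 0 whenever Visit 2 scores are missing.

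The cost is a few lines of SAS and a sensitivity interval about 1 to 2% wider. Data collection, analysis populations, the margin and the primary analysis do not change.
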